#### **5.4 Interruption or discontinuation of treatment**

For patients who are unable to tolerate the protocol-specified dosing schedule, dose adjustments are permitted in order to keep the patient on study drug. If administration of BKM120 must be interrupted because of unacceptable toxicity, drug dosing will be interrupted or modified according to rules described in Table 9. Toxicity will be assessed using the NIH-NCI Common Terminology Criteria for Adverse Events, version 4.0.

[http://evs.nci.nih.gov/ftp1/CTCAE/CTCAE\\_4.03\\_2010-06-14\\_QuickReference\\_8.5x11.pdf](http://evs.nci.nih.gov/ftp1/CTCAE/CTCAE_4.03_2010-06-14_QuickReference_8.5x11.pdf)

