#### **5.5 Dose-Limiting Toxicity**

Toxicity will be assessed using the NCI Common Toxicity Criteria for Adverse Events, version 4.0

[http://evs.nci.nih.gov/ftp1/CTCAE/CTCAE\\_4.03\\_2010-06-14\\_QuickReference\\_8.5x11.pdf](http://evs.nci.nih.gov/ftp1/CTCAE/CTCAE_4.03_2010-06-14_QuickReference_8.5x11.pdf) unless

otherwise specified (e.g., hyperglycemia). A dose-limiting toxicity (DLT) is defined as an adverse event or abnormal laboratory value assessed as unrelated to disease, disease progression, inter-current illness, or concomitant medications, and occurs < 28 days following the last dose of BKM120, and meets any of the criteria listed in Table 9.

Whenever a patient experiences toxicity that fulfills the criteria for a DLT (or a potential DLT), treatment with BKM120 will be interrupted (if not otherwise specified) and the toxicity will be followed up as described in section 5.3. Exceptions are CTCAE grade 2 hyperglycemia and CTCAE grade 2 mood alteration, where BKM120 treatment will be continued under appropriate co-medication. The criteria for dose-limiting toxicities are outlined in Table 9.

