Metabolic/Laboratory	If amylase and/or lipase $\geq$ CTCAE grade 3 ( $> 2 \times$ ULN) has been demonstrated, these parameters must be assessed once at 2 to 4 days and once again at 7 days ( $\pm 1$ day) and be repeated twice a week until resolution to $\leq$ CTCAE grade 2 to allow for initiation of re-treatment, and then at least weekly until either resolution to $\leq$ CTCAE grade 1 or until stabilization. A CT scan or other imaging study to assess the pancreas, liver, and gallbladder must be performed within 1 week of the first occurrence of any $\geq$ CTCAE grade 3 of amylase or lipase. In patients with serum triglycerides $\geq 500$ mg/dL, urine amylase needs to be tested in addition.
Endocrine (no CTCAE grading; refer to Table 15 for definition of grades)	For details of the follow-up and treatment of $\geq$ grade 2 hyperglycemia refer to Table 15.

TOXICITY	FOLLOW-UP EVALUATION
Cardiac	
Patient who experience QTc prolongation should be followed as per Table 11.
 
In addition, patients who experience ECG abnormalities indicative of an ischemic cardiac event, ECGs should be repeated at least twice a week until normalization or stabilization of ECG findings.
 
If troponin <math>\geq</math> CTCAE grade 3 has been demonstrated, this parameter must be repeated twice a week until resolution to <math>\leq</math> CTCAE grade 1 to allow for initiation of re-treatment, and then at least weekly until either resolution or until stabilization.

Neurotoxicity	
Patients who experience neurotoxicity should be followed as per Table 11.

Mood alteration
 
<math>\geq</math> grade 2
 
Note: For grade 2 Anxiety only, if worsened from baseline
	
For patient who experience <math>\geq</math> grade 2 mood alteration a psychiatrist must be consulted for diagnosis and determination of most appropriate medical treatment. Patients must be followed twice weekly by patient self-rating mood scale and be seen weekly by the psychiatrist until resolved <math>\leq</math> grade 1 or baseline (for anxiety).
 
Continue to test weekly by mood scale until resolution to baseline or stabilization
 
Refer to Table 12 for more details.

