### **5.14 Criteria for Removal from Study Treatment and/or Study Itself**

For patients who are unable to tolerate the protocol-specified dosing schedule, dose adjustments are permitted in order to keep the patient on study drug. If administration of BKM120 must be interrupted because of unacceptable toxicity, drug dosing will be interrupted or modified according to rules described in Table 11. Toxicity will be assessed using the NIH-NCI Common Terminology Criteria for Adverse Events, version 4.0.

[http://evs.nci.nih.gov/ftp1/CTCAE/CTCAE\\_4.03\\_2010-06-14\\_QuickReference\\_8.5x11.pdf](http://evs.nci.nih.gov/ftp1/CTCAE/CTCAE_4.03_2010-06-14_QuickReference_8.5x11.pdf)

The reason for study treatment discontinuation and/or study removal and the date the participant was removed must be documented in the case report form (CRF). Alternative care options will be discussed with the participant.

Reasons that a patient may discontinue study treatment and/or discontinue participation in a clinical study are considered to constitute one of the following:

1. adverse event(s)
2. abnormal laboratory value(s)
3. abnormal test procedure result(s)

4. disease progression
5. protocol violation
6. subject withdrew consent
7. lost to follow-up
8. administrative problems
9. death

A QACT Treatment Ended/Off Study Form should be filled out when a participant completes study treatment and again when the participant comes off study. This form can be found on the QACT website or obtained from the QACT registration staff.

In the event of unusual or life-threatening complications, investigators must immediately notify the Overall PI, [name] at [contact] or page at [contact].

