
Grade 2 (>160 – 250 mg/dL) [> 8.9 - 13.9 mmol/L]
	
 
• If signs or symptoms of hyperglycemia (for example, mental status changes, excessive thirst, polyuria) manage as for Grade 3 hyperglycemia (see below).
 
• If asymptomatic, maintain dose and re-check FPG within 24 hours. If grade worsens or improves then follow specific grade recommendations. If FPG remains at Grade 2:               
 
• maintain dose level and monitor FPG at least weekly until FPG resolves to ≤ Grade 1
 
• initiate or intensify medication with appropriate anti-diabetic treatment such as metformin; consider adding a second oral agent if no improvement after several days
 
• instruct patient to follow dietary guidelines according to local and/or institutional standards for management of diabetes mellitus (such as those provided by the American Diabetes Association) during the study
 
• If FPG does not resolve to ≤ Grade 1 within 14 days after institution of appropriate anti-diabetic treatment reduce BKM120 by 1 dose level
 
 
 
 
Continue with anti-diabetic treatment and check FPG at least weekly for 8 weeks, then continue checking at least every 2 weeks

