
Grade 3 (> 250 - 500 mg/dL) [> 13.9 - 27.8 mmol/L]
	
 
• Omit BKM120, initiate or intensify medication with appropriate anti-diabetic treatment, re-check FPG within 24 hours. If grade worsens or improves then follow specific grade recommendations. If FPG remains at Grade 3:               
 
• administer intravenous hydration and intervention for electrolyte/ketoacidosis/hyperosmolar disturbances as clinically appropriate
 
• continue to omit BKM120
 
• monitor FPG at least twice weekly until FPG resolves to ≤ Grade 1
 
• If FPG resolves to ≤ Grade 1 in 7 days or less, then re-start BKM120 and ↓ 1 dose level
 
• If FPG remains greater than Grade 1 severity for more than 7 days, then discontinue patient from BKM120
 
• initiate or continue anti-diabetic treatment as appropriate                   
 
• instruct patient to follow dietary guidelines according to local and/or institutional standards for management of diabetes mellitus (such as those provided by the American Diabetes Association) during the study
 
• consider use of oral anti-hyperglycemic therapy such as metformin
 
 
 
• check FPG at least weekly for 8 weeks, then continue checking at least every 2 weeks
 
 
 
 
For non-fasting plasma glucose >250-500 mg/dL (> 13.9 - 27.8 mmol/L) accompanied by signs/symptoms of hyperglycemia (for example, mental status changes, excessive thirst, polyuria), or presence of blood or urine ketones, omit BKM120 and following guidance for management of Grade 3 fasting plasma glucose (FPG)

Recommended Dose Modifications for BKM120	
Worst toxicity (CTCAE Grade)**	Recommended Dose Modifications

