### 7.1.1.3 Hyperglycemia

In preclinical studies, insulin/glucose homeostasis was impacted in various species (mice, rats, dogs), as expected from the mode of action of BKM120. In both rats and dogs, at the doses used in the 4-week studies, these effects were minimal. However, in mice treated at high doses (30 or 60 mg/kg/day) a clear induction of insulin resistance/insensitivity was observed, without clear influence of the dose or the time point of testing. Histopathologically, pancreas and liver showed changes which are in concordance with this activity.

Grade 4 Hyperglycemia was also observed in an ongoing Phase Ia study of BKM120 in patients with solid tumors (CBKM120X2101). Therefore, no patients with uncontrolled diabetes mellitus will be enrolled in this study. In all patients, fasting plasma glucose will be obtained at screening and will be monitored throughout the trial. For the treatment of glucose disturbances occurring under BKM120 treatment investigators are advised to adhere to the protocol guidelines outlined in Table 11.

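### Section 5.5 keeps BKM120 going in all grade 2 hyperglycemia, but Table 11 says to omit it when grade 2 is symptomatic, and five of seven related table references do not lead to Table 11

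*Combined protocol and SAP*

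**What the plan says.** Section 5.5 makes interruption of BKM120 the default for a DLT or potential DLT. It then states: "Exceptions are CTCAE grade 2 hyperglycemia and CTCAE grade 2 mood alteration, where BKM120 treatment will be continued under appropriate co-medication". Symptoms are not mentioned, and the sentence does not refer to Table 11.

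Table 11 (Section 6) splits grade 2 FPG, defined there as above 160 and up to 250 mg/dL, by symptoms:

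- Without symptoms: "If asymptomatic, maintain dose and re-check FPG within 24 hours".
- With symptoms: "If signs or symptoms of hyperglycemia (for example, mental status changes, excessive thirst, polyuria) manage as for Grade 3 hyperglycemia (see below".
- The grade 3 row that then applies opens: "Omit BKM120, initiate or intensify medication with appropriate anti-diabetic treatment, re-check FPG within 24 hours".

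The same FPG block is printed a second time at the end of Table 11, with the same split.

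Two places name Table 11 as the source of the dosing rules. Section 5.14 says "drug dosing will be interrupted or modified according to rules described in Table 11", and Section 7.1.1.3 says "investigators are advised to adhere to the protocol guidelines outlined in Table 11". Section 5.4 gives the Section 5.14 instruction with another table number: "drug dosing will be interrupted or modified according to rules described in Table 9". The Endocrine row of Table 10 sends the reader elsewhere again: "grade 2 hyperglycemia refer to Table 15".

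**The concern.** The two texts give opposite dosing instructions for the same patient. Read literally, Section 5.5 keeps someone with grade 2 glucose and, say, mental status changes or polyuria on the drug that is probably causing it. Table 11 would have it held.

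Hyperglycemia is not incidental in this trial. Section 2.2.8.6 describes it as an on-target effect of BKM120, and Section 2.2.8.2 lists it among the DLTs of the single-agent study. Section 5.8.2 adds 8 mg IV dexamethasone with cisplatin, and Section 2.2.8.7 notes that systemic corticosteroids raise the risk of hyperglycemia. The study calendar measures fasting glucose at every listed treatment visit, so grade 2 values will be detected and acted on.

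The wrong table references make this worse. In Sections 5.4 to 5.6, where an investigator handling a toxicity would look first, none of the references for hyperglycemia or for the general interruption rules reaches Table 11.

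**Working it through.** No sample-size or power figure is at issue. The check compares the texts and then counts the references.

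**1. The two rules side by side**

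| Situation | Section 5.5 | Table 11 |
|---|---|---|
| FPG above 160 to 250 mg/dL, no symptoms | Continue BKM120 with co-medication | Maintain dose, re-check within 24 hours |
| FPG above 160 to 250 mg/dL, with symptoms | Continue BKM120 with co-medication | Manage as grade 3: omit BKM120 |
| Grade 2 mood alteration | Continue BKM120 with co-medication | Maintain dose with co-medication |

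Rows 1 and 3 agree and row 2 conflicts. Because the mood half of the exception matches Table 11, the glucose half looks like a missing qualifier rather than a deliberate choice.

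**2. Does any wording in Section 5.5 remove the conflict?** The parenthesis that allows for other specifications belongs to the default of interrupting. The exception is a separate, unqualified sentence. No precedence rule is stated.

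**3. Table references.** The set is every reference to a table for BKM120 interruption rules in general, or for hyperglycemia grading or management.

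| Place | Table named | What that table holds | Reaches Table 11? |
|---|---|---|---|
| 2.2.8.6 | 5 | Hyperglycemia incidence in earlier studies | No |
| 5.4 | 9 | DLT criteria | No |
| Table 10, Endocrine (grade definitions) | 15 | Pneumonitis management | No |
| Table 10, Endocrine (follow-up and treatment) | 15 | Pneumonitis management | No |
| 5.14 | 11 | Dose modification | Yes |
| 7.1.1.3 | 11 | Dose modification | Yes |
| 7.1.1.4 | 5 | Hyperglycemia incidence in earlier studies | No |

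References that miss: 1 + 1 + 2 + 1 = 5 of 7, in 4 of 6 places.

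**4. Sensitivity to the set chosen**

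- Hyperglycemia references only (dropping 5.4 and 5.14): 5 − 1 = 4 of 7 − 2 = 5 miss.
- Wider set, adding the QTc and neurotoxicity references in Table 10 (both Table 11), the rash reference there (Table 6) and the dose-level reference in Table 15 (Table 11): 5 + 1 = 6 of 7 + 4 = 11 miss.

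**5. DLT status.** Table 9 counts grade 2 hyperglycemia that has not returned to grade 0 within 14 days. A Table 9 footnote also counts a lower-grade event that interrupts more than 7 doses. Which text is followed could therefore matter for a DLT call, but the direction cannot be fixed from the documents, for three reasons:

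- Holding the drug may itself change the glucose course.
- The 7-day restart and discontinuation rules in the grade 3 row sit under the condition that FPG stays at grade 3.
- Section 5.6 names interruption and permanent discontinuation as separate things.

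No DLT effect is claimed.

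**The case against.** The strongest reply is that the documents mostly settle this themselves. Section 5.5 defines DLTs, while Section 6 holds the dosing rules and prints the glucose block twice. Sections 5.14 and 7.1.1.3 both send the reader to it. A specific rule normally refines a general one, and Table 11 in effect moves symptomatic grade 2 into grade 3 management. Section 5.12.11 also lists interruption among the possible treatments of any adverse event, so a clinician facing mental status changes is not bound to Section 5.5 alone.

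Several smaller points are fair:

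- Table 11 heads its actions as recommended and Section 7.1.1.3 only advises adherence, so Table 11 should not be called an order without qualification.
- Table 11 does not make clear how long a symptomatic grade 2 patient stays off drug after the 24-hour re-check.
- The share of wrong references depends on the set counted.
- A reader sent to a pneumonitis table will notice the mistake.
- No effect on the maximum tolerated dose (MTD) is shown, so this is closer to a drafting inconsistency than a design choice.

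These points limit the weight of the finding but do not remove the contradiction. Section 5.14 says dosing will follow Table 11, and the instruction to omit is explicit. Section 5.5 says the opposite without citing Table 11. Preferring the specific rule is a sensible inference, but the protocol does not state it. A reader who notices a wrong reference still has to find the right table.

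**Conclusion.** The concern holds. For any patient with symptomatic FPG above 160 and up to 250 mg/dL, Section 5.5 continues BKM120 and Table 11 omits it. Five of the seven relevant references, as defined above, do not lead to Table 11; on the narrower and wider sets the figures are 4 of 5 and 6 of 11.

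The conclusion rests on reading the Section 5.5 exception as written and on the absence of any precedence rule. The documents give no rate of symptomatic grade 2 hyperglycemia, so how many patients would be affected is unknown. The point should be corrected on patient-safety grounds. It does not threaten the primary analysis.

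**What to change.** In Section 5.5, limit the hyperglycemia exception to asymptomatic grade 2, and add one sentence saying that symptomatic grade 2 is managed per Table 11, with BKM120 omitted.

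In the same amendment, change these five references to Table 11:

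- Section 2.2.8.6 (now Table 5)
- Section 5.4 (now Table 9)
- Table 10, Endocrine row, both references (now Table 15)
- Section 7.1.1.4 (now Table 5)

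The sentence just before the exception in Section 5.5 sends toxicity follow-up to Section 5.3, although follow-up is in Section 5.6. It can be corrected at the same time.

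Leave the Table 9 glucose criteria and the rule on more than 7 interrupted doses as they are. The amendment need not take a position on whether permanent discontinuation counts as an interruption.

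The cost is one qualifier, one sentence and five corrected table numbers. There are no added tests and no change to cohort size. Symptomatic patients will have BKM120 held, as Table 11 already provides.

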**Table 9: Criteria for Defining Dose-Limiting Toxicities**

TOXICITY	ANY OF THE FOLLOWING CRITERIA
Hematologic a	≥ CTCAE grade 3 neutropenia for > 7 consecutive days
	CTCAE grade 3 thrombocytopenia for > 7 consecutive days
	CTCAE grade 4 thrombocytopenia
	Febrile neutropenia (ANC < 1.0 x 10  /L, fever ≥ 38.5°C)
Renal	Serum creatinine ≥ 2.0 x ULN to ≤ 3.0 x ULN for > 7 consecutive days
	> CTCAE grade 3 serum creatinine
Hepatic b	Total bilirubin ≥ 2xULN to ≤ 3.0 x ULN for > 7 consecutive days
	> CTCAE grade 3 total bilirubin
	CTCAE grade 3 AST or ALT for > 7 consecutive days
	CTCAE grade 4 AST or ALT
Endocrine	Grade 2 hyperglycemia (confirmed with a repeat FPG within 24 hours) that does not resolve to grade 0 within 14 consecutive days (after initiation of glimepiride, metformin or glibenclamide)
	≥ Grade 3 hyperglycemia (confirmed with a repeat FPG within 24 hours)
Metabolic/Laboratory	CTCAE grade 3 asymptomatic amylase and/or lipase, not reversible to ≤ CTCAE grade 2 for > 7 consecutive days
	CTCAE grade 4 asymptomatic amylase and/or lipase
Pancreatitis	≥ CTCAE grade 2
Cardiac	Cardiac toxicity ≥ CTCAE grade 3 or cardiac event that is symptomatic or requires medical intervention
	Clinical signs of cardiac disease, such as unstable angina or myocardial infarction, or Troponin ≥ CTCAE grade 3
Neurotoxicity	≥ 1 CTCAE grade level increase
Mood alteration	CTCAE grade 2 mood alteration that does not resolve to ≤ grade 1 within 14 days despite medical treatment (for Anxiety only, if worsened from baseline)
	≥ CTCAE grade 3 mood alteration
Dermatologic	Any phototoxicity ≥ CTCAE grade 2, or skin toxicity (rash) resulting in interruption of BKM120 for > 21 consecutive days
Other adverse events	≥ CTCAE grade 3 adverse events (excluding ≥ CTCAE grade 3 elevations in

	alkaline phosphatase)
	≥ CTCAE grade 3 vomiting or CTCAE grade 3 nausea despite the use of standard anti-emetics
	≥ CTCAE grade 3 diarrhea despite the use of optimal anti-diarrhea treatments
	CTCAE grade 3 fatigue (asthenia) for > 7 consecutive days CTCAE grade 4 fatigue (asthenia)

a ≥ CTCAE grade 3 anemia will not be considered DLT unless judged to be a hemolytic process secondary to study drug. ≥ CTCAE grade 3 lymphopenia will not be considered DLT unless clinically significant.
 
b For any grade 3 or 4 hepatic toxicity that does not resolve within 7 days to ≤ grade 1 (or ≤ grade 2 if liver infiltration with tumor present), an abdominal CT scan has to be performed to assess if it is related to disease progression.
 
A single patient is assumed not to tolerate the dose if he/she experiences at least one DLT. If a lower grade AE leads to a dose interruption of more than 7 doses of BKM120, this AE will be considered as DLT.
 
If the 2nd occurrence of an initially non-dose limiting toxicity (e.g., grade 3 AST that resolved to ≤ grade 1 within 7 days at 1st occurrence) leads to a dose reduction ( Section 6) within 28 days of the first dose of BKM120, this will be considered a DLT.
	

The investigator must notify the sponsor immediately of any unexpected ≥ CTCAE grade 3 adverse events or laboratory abnormalities. Prior to enrolling patients into a higher dose level, ≥ CTCAE grade 2 adverse events will be reviewed for all patients at the current dose level.

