#### 5.12.11 Adverse events

Tolerability will be assessed using the NCI Common Toxicity Criteria for Adverse Events, version 4.0

[http://evs.nci.nih.gov/ftp1/CTCAE/CTCAE\\_4.03\\_2010-06-14\\_QuickReference\\_8.5x11.pdf](http://evs.nci.nih.gov/ftp1/CTCAE/CTCAE_4.03_2010-06-14_QuickReference_8.5x11.pdf)

Information about all adverse events, whether volunteered by the subject, discovered by investigator questioning, or detected through physical examination, laboratory test or other means, will be collected and recorded and followed as appropriate.

An adverse event is the appearance or worsening of any undesirable sign, symptom, or medical condition occurring after starting the study drug even if the event is not considered to be related to study drug. Medical conditions/diseases present before starting study drug are only considered adverse events if they worsen after starting study drug. Abnormal laboratory values or test results constitute adverse events only if they induce clinical signs or symptoms, are considered clinically significant, or require therapy.

The occurrence of adverse events should be sought by non-directive questioning of the patient at each visit during the study. Adverse events also may be detected when they are volunteered by the patient during or between visits or through physical examination, laboratory test, or other assessments. As far as possible, each adverse event should be evaluated to determine:

1. the severity grade (mild, moderate, severe) or (grade 1-4)
2. its relationship to the study drug(s) (suspected/not suspected)
3. its duration (start and end dates or if continuing at final exam)
4. action taken (no action taken; study drug dosage adjusted/temporarily interrupted; study drug permanently discontinued due to this adverse event; concomitant medication taken; non-drug therapy given; hospitalization/prolonged hospitalization)
5. whether it constitutes a serious adverse event (SAE)

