## 6. DOSING DELAYS/DOSE MODIFICATIONS

**Table 11: BKM120 dose level modification guidelines: Criteria for interruption and re-initiation of BKM120 treatment**

Recommended Dose Modifications for BKM120	
Worst toxicity (CTCAE Grade)**	Recommended Dose Modifications
No toxicity	Maintain dose level
HEMATOLOGICAL	
Neutropenia (ANC)	
Grade 1 (ANC < LLN – 1.5 x 10  /L) Grade 2 (ANC < 1.5 – 1.0 x 10  /L)	Maintain dose level
Grade 3 (ANC < 1.0 – 0.5 x 10  /L) Grade 4 (ANC < 0.5 x 10  /L)	Omit dose until resolved to ≤ Grade 1, then: 
 
• If resolved in ≤ 7 days, then maintain dose level
 
• If resolved in > 7 days, then ↓ 1 dose level
 

Febrile neutropenia (ANC < 1.0 x 10  /L, fever ≥ 38.5°C)	Omit dose until resolved, then ↓ 1 dose level
Thrombocytopenia	
Grade 1 (PLT < LLN – 75 x 10  /L) Grade 2 (PLT < 75 – 50 x 10  /L)	Maintain dose level
Grade 3 (PLT < 50-25 x 10  /L)	Omit dose until resolved to ≤ Grade 1, then: 
 
• If resolved in ≤ 7 days, then maintain dose level
 
• If resolved in > 7 days, then ↓ 1 dose level
 

Grade 4 (PLT < 25 x 10  /L)	Omit dose until resolved to ≤ Grade 1, then ↓ 1 dose level

Recommended Dose Modifications for BKM120	
Worst toxicity (CTCAE Grade)**	Recommended Dose Modifications
HEPATIC	
Bilirubin (*for patients with Gilbert Syndrome these dose modifications apply to changes in direct bilirubin only)	Will be fractionated if elevated
Grade 1 (> ULN – 1.5 x ULN)	Maintain dose level with LFTs* monitored as per protocol
Grade 2 (> 1.5 – 3.0 x ULN) with ALT or AST ≤ 3.0 x ULN	Omit dose until resolved to ≤ Grade 1, then: 
 
• If resolved in ≤ 7 days, then maintain dose level
 
• If resolved in > 7 days, then ↓ 1 dose level
 

Grade 3 (> 3.0 – 10.0 x ULN) with ALT or AST ≤ 3.0 x ULN	Omit dose until resolved to ≤ Grade 1, then: 
 
• If resolved in ≤ 7 days, ↓ 1 dose level
 
• If resolved in > 7 days discontinue patient from study treatment
 

Grade 4 (> 10.0 x ULN)	Omit dose and discontinue patient from study treatment
AST or ALT	
Grade 1 (> ULN – 3.0 x ULN)	Maintain dose level with LFTs* monitored as per protocol

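### Table 9's bilirubin and creatinine rows skip grade 3, so the same laboratory value can be classified as dose-limiting or not

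*Combined protocol and SAP*

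**What the plan says.** Section 5.5 makes an adverse event or abnormal laboratory value a DLT if, among other conditions, it "meets any of the criteria listed in Table 9". The relevant Table 9 rows each have a lower band and an upper criterion.

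- Renal: "Serum creatinine ≥ 2.0 x ULN to ≤ 3.0 x ULN for > 7 consecutive days", then "> CTCAE grade 3 serum creatinine".
- Hepatic (bilirubin): "Total bilirubin ≥ 2xULN to ≤ 3.0 x ULN for > 7 consecutive days", then "> CTCAE grade 3 total bilirubin".

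Table 11 in section 6 supplies the bilirubin grades: "Grade 3 (> 3.0 – 10.0 x ULN) with ALT or AST ≤ 3.0 x ULN" and "Grade 4 (> 10.0 x ULN". It has no creatinine row, and the documents do not state the CTCAE range for grade 3 creatinine.

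Three other provisions bear on the point.

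- The Other adverse events row of Table 9 counts adverse events of grade 3 or worse. It excludes only alkaline phosphatase elevations.
- The notes under Table 9 make a lower-grade AE a DLT if it costs the patient more than seven BKM120 doses. They also give, as an example of a toxicity that is not dose-limiting at first occurrence, a grade 3 AST that settles to grade 1 or less within 7 days.
- Section 5.12.11 says: "Abnormal laboratory values or test results constitute adverse events only if they induce clinical signs or symptoms". It then adds two alternative routes, clinical significance or a need for therapy.

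**The concern.** A DLT definition should be ordered: at a given duration, a worse value should not be less dose-limiting than a milder one. Taken alone, the bilirubin and creatinine rows break that order. A sustained value in the 2.0-3.0 x ULN band counts, a sustained grade 3 value does not, and grade 4 counts again. Whether grade 3 counts therefore depends on provisions elsewhere that can be read in different ways.

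The MTD is the primary objective, and section 5.3 makes the DLT its basis. Two investigators, or a site and the monitoring committee, could classify the same patient differently, and with three to six patients per level one patient can decide the outcome. Both laboratory values are relevant to this combination: section 5.8.2 describes cisplatin as nephrotoxic, and section 2.2.8.3 reports liver test changes with BKM120.

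**Working it through.** **1. The Hepatic row against Table 11's grades.** Bilirubin values and durations were classified under three readings:

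- (A) the bilirubin criteria alone;
- (B) A plus the Other adverse events row, taken to cover grade 3 bilirubin;
- (C) A plus the note on more than seven interrupted doses. This uses Table 11's instruction to omit BKM120 until grade 1 or less, and daily dosing (section 5.1).

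| Bilirubin (x ULN) | Duration | A | B | C |
|---|---|---|---|---|
| 2.5 | 7 days | no | no | no |
| 2.5 | 8 days | DLT | DLT | DLT |
| 3.1, 5 or 10 | 7 days | no | DLT | no |
| 3.1, 5 or 10 | 8 or 14 days | no | DLT | DLT |
| 10.1 | any | DLT | DLT | DLT |

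Under A the order is reversed at 8 days. Under B or C it is not. The three readings disagree for every grade 3 value, so the question is whether B or C is secure.

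**2. Reading B.** If the Other adverse events row overrode the organ-specific rows, any grade 3 AST would be a DLT at once. That contradicts the example under Table 9 of a grade 3 AST that is initially not dose-limiting. It would also leave the 7-day limits for grade 3 AST/ALT and grade 3 thrombocytopenia with no effect. In addition, a laboratory value must first qualify as an adverse event under section 5.12.11.

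**3. Reading C.** The note applies to a lower-grade AE, and the term is not defined; whether grade 3 qualifies is open. If the note is applied broadly, 1.8 x ULN for 8 days also becomes a DLT, because Table 11 omits the dose from grade 2 (above 1.5 x ULN). The band's lower limit of 2 x ULN then does no work. For creatinine the route is weaker still. Section 6.1 handles renal toxicity by changing cisplatin, and section 5.1 continues BKM120 when cisplatin is held. BKM120 may therefore not be interrupted unless the creatinine value is managed under Table 11's row for other non-hematological adverse events.

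**4. Effect on decisions (Table 7).** One reclassified patient turns 0/3 (escalate) into 1/3 (enter three more), or 1/6 (escalate) into 2/6 (stop; the previous level is the MTD). This needs no assumed rate.

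**5. Effect on escalation probability.** Section 13's table follows from

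P(escalate) = (1-p)^3 + 3p(1-p)^2 x (1-p)^3.

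At p = 20, 30, 40, 50 and 60% this gives .709, .494, .309, .172 and .082. The plan states .71, .49, .31, .17 and .08, so its table reproduces.

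Now assume that otherwise uncounted grade 3 bilirubin or creatinine events occur in a fraction q of patients, independently of other DLTs at rate b. The full rate is t = 1 - (1-b)(1-q).

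| b | q | t | P(escalate) at b | P(escalate) at t |
|---|---|---|---|---|
| 20% | 2% | 21.6% | .709 | .674 |
| 20% | 5% | 24.0% | .709 | .622 |
| 20% | 10% | 28.0% | .709 | .536 |
| 30% | 2% | 31.4% | .494 | .466 |
| 30% | 5% | 33.5% | .494 | .425 |
| 30% | 10% | 37.0% | .494 | .360 |

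For example, at t = 24%: .76^3 + 3 x .24 x .76^5 = .439 + .183 = .622.

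**The case against.** The strongest reply is that the protocol read as a whole already counts these patients. Meeting any one Table 9 criterion is enough. The only exclusion in the Other adverse events row is a laboratory value, which suggests that laboratory values are otherwise within it. A bilirubin that obliges the investigator to omit BKM120 is also hard to call clinically insignificant. Separately, a grade 3 bilirubin lasting 8 days costs more than seven daily doses. On that route only grade 3 resolving within 7 days stays uncounted, and a 2-3 x ULN value of that duration is not a DLT either.

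This carries weight. A reader might infer from the rows that a sustained grade 3 bilirubin or creatinine is definitely not dose-limiting. The documents do not support that, because either provision can capture it. Nor do they establish that it is dose-limiting, for the reasons in steps 2 and 3. The alkaline phosphatase exclusion does not settle the matter: that test has no row of its own, so the exclusion fits equally well with a row meant only for unlisted toxicities.

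Three further objections stand in part.

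- The sign may be a slip, or a reading error in the PDF text. Neighbouring criteria show the greater-or-equal sign correctly, which makes a reading error less likely but does not exclude it.
- The renal gap as a range rests on an assumption: that grade 3 creatinine begins just above 3.0 x ULN, inferred from the band's upper limit.
- A reader might take Table 3 as evidence that grade 3 bilirubin is common. Section 2.2.8.3 says the liver changes were mostly transaminase increases, and the AST/ALT criteria have no such gap.

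**Conclusion.** The point holds as an inconsistency in the definition behind the primary endpoint. As written, the Hepatic row has no criterion for the whole of grade 3 bilirubin (above 3.0 to 10.0 x ULN), and the Renal row skips grade 3 creatinine. The provisions that might fill the gap conflict with other parts of the protocol or rest on an undefined term. The classification is ambiguous, which is a narrower conclusion than exclusion.

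The firm consequence is that one patient's classification can change a Table 7 decision. The probability shifts are illustrations only: they assume event rates the documents do not give, independence from other DLTs, and that the events would otherwise go uncounted. At 2% the shift is small (.71 to about .67); at 10% it is material (.71 to about .54). Section 13's table is correct and unaffected, because it is indexed by the true DLT rate.

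**What to change.** First confirm the sign in the approved protocol. If the text is as shown, amend it to reconcile the Renal and Hepatic rows, the Other adverse events row, the notes under Table 9 and Table 11. After the amendment:

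- each bilirubin and creatinine value and duration has exactly one DLT classification;
- no higher value is less dose-limiting than a lower one of the same duration;
- the table states which row governs when an organ-specific row and the Other adverse events row could both apply;
- the term lower-grade AE is defined, and the grade range used for creatinine is given.

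The clinical threshold is for the sponsor and investigator to decide. Before the MTD is declared, re-read completed cohorts against the reconciled table. The cost is a short amendment and a check of laboratory values already collected; sample size and the section 13 table do not change.
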